**Table 1: Visit Windows for Analysis** 

[figure not shown]
Scheduled Visit (+/1 window days) in protocol	Target Study Day	Study Day Window for Visit in Analysis
Day 1	Day 1 (predose)	Day 1 (predose) or last non- missing assessment before pre- dose regardless of scheduled or unscheduled visits
Day 7 (±1 day)	Day 7	Day 2 - Day 10
Day 14 (+1 day)	Day 14	Day 11 - Day 17
Day 28 / last dose + 14 days (±2 day)	Day 28 (last dose date + 14 days)	>= Day 26 (last dose date +12 days)

Note: Parenthesized study day and study day window are for unscheduled visits, EOT and ET for participants who have discontinued treatment prematurely and such visit date is  $\geq 4$  days from the last dose of investigational product intake (ie, visit date – last dose date + 1 > 4).

[figure not shown]
The summary by visit will use the "analyzed records" only – at most one per participant. The data not flagged as the "analyzed record" will be included in listings. An unscheduled visit that does not fall under any analysis window will remain in the database and will be included in the listings.

[figure not shown]

[figure not shown]

[figure not shown]
Sponsor: Sage Therapeutics

[figure not shown]

[figure not shown]

[figure not shown]

Sponsor: Sage Therapeutics

[figure not shown]

[figure not shown]

Sponsor: Sage Therapeutics

# 16.0 Safety and Tolerability Analyses

All safety analyses will be performed using the safety analysis set. Baseline for safety data is defined as the last non-missing value prior to the first dose of the investigational product.

Safety and tolerability of SAGE-718 will be evaluated by treatment-emergent adverse events (TEAEs) and change from baseline vital signs, clinical laboratory analytes, electrocardiograms (ECGs), safety electroencephalogram (EEG), and responses on the Columbia–Suicide Severity Rating Scale (C-SSRS). Safety data will be listed by the participant and summarized using descriptive statistics (mean, median, range, percentages).

#### 16.1 Adverse Events

TEAEs are defined as any AEs with an onset date on or after the date of the first dose of IP or any worsening of a preexisting medical condition/AE with onset after the start of IP and throughout the study. An AE leading to treatment discontinuation is defined as an AE with action taken of the investigational product as Drug Withdrawn. AEs will be coded using the Medical Dictionary for Regulatory Activities MedDRA version 23.1.

An overall summary of TEAEs, including the number of events, reported, the number and percentage of participants reporting at least one TEAE, the number and percentage of participants reporting at least one related TEAE, Number and percentage of participants by maximum severity, the number and percentage of participants discontinuing due to an adverse event, the number and percentage of participants with at least one serious adverse event, and the number and percentage of deaths will be presented.

A breakdown of the number and percentage of participants reporting each TEAEs, categorized by System Organ Class (SOC) and preferred term (PT), will be presented. Note that counting will be by a participant, not event, and participants are only counted once within each SOC and PT.

A further tabulation of these data, categorized by relationship (to SAGE-718), will be presented. Participants with multiple events within a particular body system or preferred term will be counted under the category of their drug-related event (related and not related) within SOC and PT. Relationship to SAGE-718 is categorized as related or not related.

A summary of events reported, categorized by severity, will also be provided. Participants with multiple events within a particular SOC and PT will be counted under the category of their most severe event in the following order: severe> moderate> mild within that SOC and PT.

A summary of adverse events leading to discontinuation of SAGE-718 will be provided, grouped by body system and preferred term.

All adverse events (including non-treatment-emergent events) recorded on the CRF will be listed.

Handling of missing AE start dates is defined in Appendix-C. Missing data for severity or relatedness to treatment will not be imputed.

#### 16.1.1 Deaths and Serious Adverse Events (SAEs)

All deaths and SAEs will be provided in by-participant listings.

### 16.2 Clinical Laboratory Evaluations

Laboratory assessments for biochemistry, coagulation, hematology, urinalysis, and serology, will be collected at screening, Day -1, Day 7, Day 14, and Day 28. The clinical laboratory tests to be performed for monitoring safety are listed in **Table 4**. Laboratory assessments will be summarized (n, mean, std,

median, Q1, Q3, minimum, and maximum) along with the change from baseline by each scheduled post-baseline visit. The International System of Unit (SI) will be used.

For the laboratory results that is "< or = x", where x is a number as collected in the data, the numeric part of the result will be used in the calculation in the summary tables. The same is true if the result is presented as below limit of quantification (BLQ) and a lower limit of quantification (LLOQ) value is provided – LLOQ value will be used for calculation in the summary tables. The actual results as collected will be displayed in the listings.

Summary tables on lab parameters will include descriptive statistics for the observed values and changes from baseline by scheduled assessment timepoint in hematology, serum chemistry, coagulation, and quantitative urinalysis test results.

**Table 4 Clinical Laboratory Tests** 

Hematology	Serum Chemistry	Urinalysis	Coagulation
Hematology Red blood cell count Hemoglobin Hematocrit White blood cell count with differential Platelet count Red Blood Cell Indices (MCV, MCH, MCHC) Reflex to Red blood cell morphology if indices are abnormal	Serum Chemistry  Alanine aminotransferase Albumin Alkaline phosphatase Aspartate aminotransferase Total bilirubin Direct bilirubin Indirect bilirubin Total protein Creatinine Blood urea nitrogen Creatine kinase Gamma-glutamyl transferase	Urinalysis pH  Protein Glucose Red blood cell Nitrite Leukocyte esterase Ketones Bilirubin Urobilinogen	Coagulation  Activated partial Thromboplastin time Prothrombin time International normalized ratio
apnormai		Urobilinogen	
	Thyroid stimulating hormone (TSH)		

If a normal range is provided for the parameter, out-of-range values will be flagged as low or high, where applicable, in the participant data listings

The number and percentage of participants with potentially clinically significant (PCS) values will be provided in separate displays in hematology, serum chemistry, and liver function tests provided for such occurrence by time point.

PCS values will be identified for specific laboratory parameters as outlined in Table 5.

Liver function tests will be monitored closely for PCS values, and will be summarized for occurrence any time post-baseline for the following parameters for these PCS thresholds (for conditions involving more than one parameter, the results need to be from the same timepoint):

Alanine Aminotransferase: >3xULN, >5xULN, >10xULN Aspartate Aminotransferase: >3xULN, >5xULN, >10xULN

Alanine Aminotransferase or Aspartate Aminotransferase: >3xULN, >5xULN, >10xULN

Alkaline Phosphatase: >1.5xULN, >2xULN

Total Bilirubin: >1.5xULN, >2xULN

Total Bilirubin > 2xULN **AND** (Alanine Aminotransferase or Aspartate Aminotransferase >3xULN)
Total Bilirubin >2xULN **AND** Alkaline Phosphatase >2xULN **AND** (Alanine Aminotransferase or

Aspartate Aminotransferase >3xULN)

Any lab results considered clinically significant by the investigator will be captured as adverse events, hence will show up in AE displays.

Pregnancy test results will be listed but not summarized.

Table 5 Potentially Clinically Significant Values for Specific Laboratory Parameters

Laboratory Parameter	Gender	Units	Criteria for PCS Values (Observed values)		
			High	Low	
Hematology					
Hemoglobin	Male	g/L	>185	<115	
	Female	g/L	>170	<100	
Hematocrit	Male	Fraction of 1	>0.55	<0.385	
	Female	Fraction of 1	>0.49	<0.345	
Platelet count		10^9/L	>600	<125	
White blood cell		10^9/L	>15	<2.5	
Basophils		10^9/L	>0.5	NA	
Eosinophils		10^9/L	>1.5	NA	
Neutrophils		10^9/L	NA	<1.5	
Lymphocytes		10^9/L	>6.0	<0.5	
Monocytes		10^9/L	>1.4	NA	

Laboratory Parameter	Gender	Units	Criteria for PCS V	Criteria for PCS Values (Observed values)		
			High	Low		
Serum Chemistry						
Albumin		g/L	>70	<28		
Blood urea nitrogen		mmol/L	>10.71	NA		
Calcium		mmol/L	>2.75	<2.0		
Chloride		mmol/L	>120	<90		
Creatinine		mmol/L	>3xULN or >3x Baseline			
Gamma Glutamyl Transferase			>3xULN			
Glucose		mmol/L	>13.9	<2.8		
Sodium		mmol/L	>150	<132		
Potassium		mmol/L	>5.4	<3.3		
Protein		g/L		<45		
Bicarbonate		mmol/L	>34	<18		
		mmol/L	>120	<90		
Phosphorus		mmol/L	>1.94	<0.61		
Liver Function Tests (LFT)						
Bilirubin		μmol/L	>2xULN	NA		
Aspartate Aminotransferase		U/L	>3xULN	NA		
Alanine Aminotransferase		U/L	>3xULN	NA		
Alkaline Phosphatase		U/L	>1.5xULN	NA		

# 16.3 Physical/Neurological Examinations

The occurrence of a physical examination, Neurological examination (yes/no), and the date performed will be listed by the participant.

### 16.4 Vital Signs

Vitals for the following parameters - respiratory rate (breaths/minute), oral temperature (degrees C), supine heart rate (beats/minute), supine systolic blood pressure (mmHg), supine diastolic blood pressure (mmHg), standing heart rate (beats/minute), standing systolic blood pressure (mmHg), standing diastolic blood pressure (mmHg), – are collected at Screening and on Days -7, -1, 1, 7, 14, and 28. Descriptive summaries of observed values and changes from baseline will be provided for vital sign parameters - by scheduled assessment time point. Additionally, the number and percentage of participants with PCS and potentially clinically significant change (PCSC) values will be summarized for such occurrence any time post-baseline. Potentially clinically significant values will be identified for vital sign parameters as outlined in Table 6.

Table 6 Potentially Clinically Significant Values and Change for Vital Sign Parameters

Vital Sign	Units	Criteria for PCS Values (Observed values)		Criteria for PCSC values (Change from Baseline values)	
		High	Low	Increase	Decrease
Heart rate (supine and standing)	Beats/min	>120	<40	NA	NA
Systolic Blood Pressure (supine and standing)	mmHg	>180	<90	≥30	≥30
Diastolic Blood pressure (supine and standing)	mmHg	>110	<50	≥20	≥20
Supine - Standing Systolic Blood Pressure	mmHg	≥20			
Supine – Standing Diastolic Blood Pressure	mmHg	≥10			
Orthostatic hypotension: supine – standing SBP and DBP	mmHg	SBP ≥20 and DBP ≥10			
Possible Orthostatic hypotension: supine – standing SBP and DBP	mmHg	SBP ≥20 or DBP ≥10			

The orthostatic vital sign - the change from supine to standing (Supine – Standing) in heart rate, systolic and diastolic blood pressure – will be summarized by scheduled assessment timepoint, at 1 and 3 minutes.

Any vital signs result considered clinically significant by the investigator will be captured as adverse events, hence will show up in AE displays. All vital sign assessments along with PCS will be listed in the listing.

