- e. Other medications given at doses or in combinations that are likely to have a deleterious effect on cognitive performance, as described in the 2019 American Geriatrics Society Updated Beers® Criteria for Potentially Inappropriate Medication Use in Older Adults (American Geriatrics Society 2019)
- f. Prescribed cannabis or other THC-containing substances
- 10. Have an alcohol or drug use disorder within the past 12 months, as per DSM-5 criteria
- 11. Have a history of seizures or epilepsy, with the exception of a single episode of febrile seizures in childhood
- 12. Have current or recent suicidality, defined as follows:
 - a. Suicidal ideation within the past month, as evidenced by a score of 4 (active suicidal ideation with some intent to act, without specific plan) or 5 (active suicidal ideation with specific plan and intent) on the C-SSRS during Screening or Baseline
 - b. Suicidal behavior within the past year, as evidenced by a "Yes" on any of the 5 C-SSRS Suicidal Behavior Items (actual attempt, interrupted attempt, aborted attempt, preparatory acts, or behavior) on the C-SSRS during Screening or Baseline
 - c. Participant presents a serious risk of suicide in the opinion of the investigator
- 13. Have any of the following clinically significant medical conditions:
 - a. Any clinically significant finding on 12-lead ECG during Screening or Baseline
 - b. Supine vital signs outside of the following ranges during Screening or Baseline; vital sign measurements may be repeated once for initial values outside these ranges:
 - Heart rate <50 or >100 bpm
 - Systolic blood pressure <100 or >160 mmHg
 - Diastolic blood pressure <60 or >100 mmHg
- 14. Have a history, presence, and/or current evidence of serologic positive results for HIV-1 or HIV-2
- 15. Have a positive pregnancy test or be lactating at Screening or Day -1
- 16. Be investigative site personnel, sponsor personnel, or an immediate member of their family (spouse, parent, child, or sibling whether biological or legally adopted)

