### 16.5 12-Lead Electrocardiogram

Supine 12-lead ECGs will be performed in triplicate, and are collected on screening, days -1, 1, 7, 14, and 28. The following ECG parameters will be listed for each participant: heart rate (beats per minute), PR (msec), QRS (msec), QT (msec), and QTcF (msec).

The average of the triplicate values will be used in the summary, including baseline ECG values. The observed value at each time point and change from baseline at each post-baseline scheduled time point will be summarized. Each ECG is evaluated as 'normal', 'abnormal, not clinically significant' and 'abnormal, clinically significant'; the number and percentage of participants with at least one of the triplicate values in the categories of 'abnormal, clinically significant' and 'abnormal, not clinically significant' will be provided at baseline and each post-baseline scheduled assessment time point.

The number and percentage of participants with PCS and PCSC values will be summarized for such occurrence any time post-baseline. Potentially clinically significant values will be identified for ECG parameters as outlined in Table 7. A listing of ECG and QTcF PCS values will be provided.

Table 7 Potentially Clinically Significant Values and Change for ECG Parameters

ECG	Units	Criteria for PCS Values (Observed val	Criteria for PC (Change from		
		High	Low	Increase	Decrease
QTcF Interval	msec	>450 but <=480 >480 but <=500 >500	NA	>=30 to 60 >60	NA

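### The orthostatic counts in SAP 16.4 mix standing blood-pressure drops present before dosing with new ones; the observed-value QTcF categories in 16.5 share the weakness to a lesser degree

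*SAP*

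**What the plan says.** SAP 16.4 sets the counting rule for vital signs: "PCS and potentially clinically significant change (PCSC) values will be summarized for such occurrence any time post-baseline". Table 6 then has four rows built on the supine-minus-standing difference: a systolic drop of at least 20 mmHg, a diastolic drop of at least 10 mmHg, orthostatic hypotension ("SBP ≥20 and DBP ≥10") and possible orthostatic hypotension ("SBP ≥20 or DBP ≥10"). All four are observed-value criteria, and their change-from-baseline cells hold nothing. Systolic and diastolic pressure, both supine and standing, do have change criteria. Heart rate is marked as having none. Separately, the supine-to-standing change "will be summarized by scheduled assessment timepoint, at 1 and 3 minutes".

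SAP 16.5 uses the same rule for the ECG: "The number and percentage of participants with PCS and PCSC values will be summarized for such occurrence any time post-baseline". The QTcF observed-value categories in Table 7 are ">450 but <=480 >480 but <=500 >500" msec. The same table also counts QTcF increases from baseline of 30 to 60 msec and of more than 60 msec.

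At entry, protocol 8.2 exclusion 13b covers "Supine vital signs outside of the following ranges during Screening or Baseline". Exclusion 13a covers "Any clinically significant finding on 12-lead ECG during Screening or Baseline" and gives no QTcF limit. SAP 16.0 defines safety baseline as the last non-missing value before the first dose.

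**The concern.** All participants receive SAGE-718, so there is no control rate against which to read an any-time percentage. A participant's own pre-dose status is the only reference within the study. A row that counts a finding after dosing, whether or not it was there before, shows how many participants had the finding but not how many developed it. The population is aged 50 to 80 and about 22 are planned, so a few long-standing cases could make up most of the row.

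The plan takes account of baseline in other places. A TEAE needs onset or worsening after the start of dosing (SAP 16.1). The creatinine row of Table 5 includes a multiple of baseline. ECG interpretations are tabulated at baseline as well as afterwards (SAP 16.5). Protocol 13.6.2 promises baseline shifts for laboratory abnormalities. No comparable count is described for orthostatic status or QTcF category.

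**Working it through.** **1. Denominator.** The plan states about 22 dosed for 20 completers at 10% dropout (protocol 13.8, SAP 10.2). 20 / 0.9 = 22.2, or 23 rounded up; 20 x 1.10 = 22. Either agrees with the plan's approximate figure, so 22 is used below.

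**2. Which rows the entry criteria protect.**

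| Measure | Entry range (13b) | PCS limits (Table 6) | Change criterion |
|---|---|---|---|
| Supine heart rate, bpm | 50 to 100 | <40, >120 | none |
| Supine SBP, mmHg | 100 to 160 | <90, >180 | yes |
| Supine DBP, mmHg | 60 to 100 | <50, >110 | yes |
| Standing SBP and DBP | none | as supine | yes |
| Standing heart rate | none | <40, >120 | none |
| Four supine-minus-standing rows | none | drop of 20 and/or 10 mmHg | none |

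The supine entry ranges lie inside the PCS limits, so supine values are not the problem. The orthostatic rows and standing heart rate have neither an entry limit nor a change criterion.

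**3. Worked cases (illustrative values).** Supine 130/80 and standing 105/68 mmHg at every visit is a drop of 25/12. The supine values pass 13b. After dosing the participant is counted in all four orthostatic rows, although nothing has changed. For QTcF, 455 msec before dosing and 452 msec on Day 7 falls in the lowest observed-value category despite a 3 msec decrease. That participant adds nothing to the change categories, so for QTcF the plan does partly separate the two situations.

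**4. Size, persistent finding, no drug effect.** The prevalence p is an assumption. Expected count = 22p; chance of at least one = 1 - (1 - p)^22.

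| p | Expected count | Chance of at least one |
|---|---|---|
| 5% | 1.1 | 68% |
| 10% | 2.2 | 90% |
| 20% | 4.4 | 99% |
| 30% | 6.6 | >99% |

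Conditioning on baseline reduces each of these counts to 0.

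**5. Size, intermittent finding, no drug effect.** Let a share p be prone to drops, each showing one at any visit with probability r, over the three scheduled post-baseline visits (Days 7, 14, 28).

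- Any-time count: 22p[1 - (1 - r)^3].
- New relative to the SAP baseline: the same multiplied by (1 - r).
- Example, p = 20%, r = 0.7: 4.4 x 0.973 = 4.28 any-time; 4.28 x 0.3 = 1.28 new.
- Over p = 10% to 30% and r = 0.5 to 0.9, the any-time count is 1.9 to 6.6 and the new count 0.2 to 2.9.

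Conditioning on the single baseline value therefore removes much of the pre-existing component, but not all of it.

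**6. QTcF above 450 msec.** The distributions are assumed, stable and normal, before any screening under 13a.

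| Mean/SD, msec | Share above 450 | Expected of 22 | Chance of at least one |
|---|---|---|---|
| 410/20 | 2.3% | 0.5 | 40% |
| 420/20 | 6.7% | 1.5 | 78% |
| 425/22 | 12.8% | 2.8 | 95% |

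**The case against.** The strongest reply is that these counts are supplementary and that the information exists elsewhere. The secondary endpoint is change from baseline in vital signs, laboratory values, ECGs and C-SSRS responses, and by-visit change summaries address it. The PCS rows are added to those summaries. Orthostatic differences are summarised by time point, all vital signs are listed with their PCS status, and with about 22 participants a reader could trace by hand who met a criterion before dosing. Findings judged clinically significant become adverse events, where the treatment-emergent definition applies. All of this stands, and it limits the point to the interpretability of a descriptive table. It does not supply the missing count.

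A reader might also infer more than the documents support:

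- *That QTcF and standing blood pressure are assessed without regard to baseline.* Table 7 has change categories for QTcF, and Table 6 has them for standing systolic and diastolic pressure.
- *That a participant with a standing drop or long QTcF is certain to be eligible.* Exclusion 3 gives the investigator discretion over clinically significant comorbidity, and 13a may remove larger QTcF prolongations. Such a participant could be eligible; the text supports no more.
- *That 6 to 14 of 22 could be counted spuriously.* With independent visits, 1 - (1 - p)^3 is 27.1% at p = 10% and 65.7% at p = 30%, or 6.0 and 14.5 of 22. But if visits are independent, pre-dose status says nothing about later status, and the rate among participants negative at baseline is still 27% to 66%. That figure measures repeated looks, not pre-existing drops.
- *That the table is wrong.* It is an accurate count of observed values; the fault lies in reading it as new findings.

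**Conclusion.** The point holds for the four orthostatic rows of Table 6, which have no entry limit, no change criterion and no baseline-conditioned count in a study without a control arm. Standing heart rate has the same gap. For the observed-value QTcF categories it holds less strongly, because of the change categories in Table 7 and exclusion 13a.

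The size is about 2 to 7 of 22 participants in an orthostatic row with no drug effect. That rests on an assumed prevalence of 10% to 30% and full persistence across visits; neither figure comes from the documents. The QTcF figures are likewise illustrations. The change is worth making because it is cheap and these rows are otherwise hard to interpret. It does not bear on the validity of the primary endpoint or of the change-from-baseline summaries.

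**What to change.** In SAP 16.4 and 16.5, and in Tables 14.3.4.2 and 14.3.5.3, keep the all-participant count. For the orthostatic rows, standing heart rate and QTcF category, add:

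- the number meeting the criterion at baseline; and
- a treatment-emergent count: participants meeting the criterion after baseline among those who did not meet it at baseline. For QTcF, this is a move to a higher category than at baseline.

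A baseline by worst post-baseline shift table would serve equally well. Derive baseline status from the same standing readings (1 and 3 minutes) as the post-baseline status.

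Use the SAP baseline, the last non-missing pre-dose value. Conditioning instead on any of the four pre-dose vital-sign visits (Screening, Days -7, -1 and 1) would depart from that definition. If visits were independent, it would cut the denominator to 22 x 0.9^4 = 14.4 at p = 10%, or 22 x 0.7^4 = 5.3 at p = 30%. With the single baseline it is 22 x 0.9 = 19.8 or 22 x 0.7 = 15.4. Status at any pre-dose visit can be shown as a supportive display, since drops may be intermittent.

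The cost is SAP wording, a few table columns and a somewhat smaller denominator in the treatment-emergent column. All the data are already collected.

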### 16.5 12-Lead Electrocardiogram

Supine 12-lead ECGs will be performed in triplicate, and are collected on screening, days -1, 1, 7, 14, and 28. The following ECG parameters will be listed for each participant: heart rate (beats per minute), PR (msec), QRS (msec), QT (msec), and QTcF (msec).

The average of the triplicate values will be used in the summary, including baseline ECG values. The observed value at each time point and change from baseline at each post-baseline scheduled time point will be summarized. Each ECG is evaluated as 'normal', 'abnormal, not clinically significant' and 'abnormal, clinically significant'; the number and percentage of participants with at least one of the triplicate values in the categories of 'abnormal, clinically significant' and 'abnormal, not clinically significant' will be provided at baseline and each post-baseline scheduled assessment time point.

The number and percentage of participants with PCS and PCSC values will be summarized for such occurrence any time post-baseline. Potentially clinically significant values will be identified for ECG parameters as outlined in Table 7. A listing of ECG and QTcF PCS values will be provided.

Table 7 Potentially Clinically Significant Values and Change for ECG Parameters

ECG	Units	Criteria for PCS Values (Observed val	Criteria for PC (Change from		
		High	Low	Increase	Decrease
QTcF Interval	msec	>450 but <=480 >480 but <=500 >500	NA	>=30 to 60 >60	NA

